13.3 Dose Escalation/Expansion

The phase I study will follow a modified 3+3 design. During dose-doubling, enrollment and dose escalation of a cohort will be on the basis of the occurrence of moderate and/or dose limiting toxicities (DLTs). If dose-doubling is ended by a single DLT in cycle 1 or two occurrences of 'moderate' treatment-related

toxicity, subsequent dosing will be based on DLT only. DLT and moderate toxicity incidence will be based on toxicity events encountered during the first cycle of 8-chloro-adenosine treatment.

This modified design involves an initial accelerated dose escalation stage (dose-doubling over 'a' levels) that may be ended by a single dose-limiting toxicity (DLT) in cycle 1 or two occurrences of 'moderate' treatment-related toxicity as defined in section 13.2. During the initial accelerated stage of accrual, cohorts of up to 3 patients will be enrolled and the dose level will be escalated by increments of 100% (skipping 'b' dose levels). If two patients encounter moderate toxicity or one patient encounters DLT during cycle 1, the current dose level will be expanded and the accelerated stage will end; dose-doubling will stop. At the conclusion of the accelerated stage, dose escalation will occur over 'a' and 'b' dose levels according to the following rules*:

- If zero out of 3 evaluable patients has a DLT in cycle 1 then the next dose of 8-chloro-adenosine will be tested.
- If 1 out of 3 evaluable patients has a DLT in cycle 1, three additional patients will be assessed at the same dose of 8-chloro-adenosine.
- If 2 out of 3 patients have a DLT in cycle 1, dose escalation will cease and the next lower dose level will be expanded. Note: If 2 of 3 experience DLT on dose level -1, the trial will be stopped. Dose levels below 50mg/m² will not be considered.
- If 1 out of 6 evaluable patients has a DLT in cycle 1, then dose escalation to the next dose of 8-chloro-adenosine will continue.
- If 2 or more out of 6 patients have a DLT in cycle 1, dose escalation will cease and the next lower dose level will be expanded. Note: If 2 of 6 experience DLT on dose level -1, the trial will be stopped. Dose levels below 50mg/m² will not be considered.

The highest dose level that produces $\leq 1/6$ DLTs in cycle 1 will be the maximum tolerated dose (MTD). Patients may continue therapy unless there is unacceptable toxicity, disease relapse/progression or withdrawal of consent.

*: Note: Dose de-escalation, escalation or cohort expansion will only take place after 3 patients are fully assessed (assuming the first two patients have yet to experience a DLT) using the Common Terminology Criteria for Adverse Events (CTCAE) of the National Cancer Institute (NCI) version 4.03 following the completion of cycle 1.

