
Statistical Considerations:
 
Study Design
 
Phase I: The primary objective of the phase I study is to determine the recommended phase II dose (RP2D) of 8-chloro-adenosine when given as a single agent, in patients with relapsed or refractory acute myeloid or lymphoblastic leukemia. The phase I study will follow a modified 3+3 design for enrollment with dose escalation, or expansion of a cohort on the basis of the occurrence of dose limiting toxicities (DLTs) during cycle 1. This modified design involves an initial accelerated dose escalation stage (dose-doubling from an initial dose of 100mg/m² to 800mg/m²) that may be ended by a single DLT in cycle 1 or two occurrences of ‘moderate’ treatment-related toxicity. During the initial accelerated stage of accrual, cohorts of up to 3 patients will be enrolled and the dose level will be escalated by increments of 100%. The accelerated stage will end when two patients encounter moderate toxicity or when one patient encounters DLT during cycle 1. At the conclusion of the accelerated stage, the dose escalation will occur according to the standard 3+3 rules: The highest dose level that produces $\leq 1/6$ DLTs in cycle 1 will be the maximum tolerated dose (MTD). The RP2D of 8-chloro-adenosine will generally be the MTD, but it may be less than the MTD based on a review of available data/cumulative toxicities from phase I. The RP2D identified in the phase I portion of the study will be brought forward for further activity evaluation in the phase II portion.

Phase I/ Evaluable for Toxicity: Patients will be considered evaluable for toxicity if they receive any study drug. To be evaluable in the context of dose escalation, a patient must receive at least 80% of 8-chloro-adenosine and be followed for at least 28 days during cycle 1 or experience a DLT during the first cycle of therapy. All patients who are not evaluable for dose limiting toxicity will be replaced. Patients who are replaced with a moderate toxicity will be used in the decision to stop the accelerated dose-doubling stage.

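### Section 13.3 ends dose-doubling on two occurrences or on two patients with moderate toxicity, and with two such patients and 0/3 DLTs it supports both expanding 400 mg/m² and opening 600 mg/m²

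*Combined protocol and SAP*

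**What the plan says.** Section 5.3 sends the reader to Section 13.3 for the escalation rules. There the accelerated, dose-doubling stage is described as one "that may be ended by a single dose-limiting toxicity (DLT) in cycle 1 or two occurrences of" moderate toxicity; a second sentence of 13.3 and one in 13.1 use the same unit. The sentence of 13.3 that prescribes what to do counts patients: "If two patients encounter moderate toxicity or one patient encounters DLT during cycle 1, the current dose level will be expanded". It goes on to close the accelerated stage. The synopsis (Statistical Considerations) carries both units. Its description uses occurrences, and its prescriptive sentence is "The accelerated stage will end when two patients encounter moderate toxicity or when one patient encounters DLT during cycle 1". The synopsis also has a rule on replaced patients: "Patients who are replaced with a moderate toxicity will be used in the decision to stop the accelerated dose-doubling stage".

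Once the stage has ended, 13.3 applies a list of DLT rules over all dose levels, including the intermediate (b) levels. Its first line is "If zero out of 3 evaluable patients has a DLT in cycle 1 then the next dose of 8-chloro-adenosine will be tested". The other lines cover 1/3, 2/3, 1/6 and 2 or more of 6; there is no 0/6 line. Three additional patients are prescribed only after 1/3 DLTs. The note to 13.3 says "cohort expansion will only take place after 3 patients are fully assessed", and it ties escalation to the same moment.

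Section 13.1 sets the starting dose at 400 mg/m² (level 3a) with amendment v07. Table 5.3.1 lists 600 mg/m² (3b) and 800 mg/m² (4a) above it.

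**The concern.** From a 400 mg/m² start, 400 to 800 is the only doubling step left. The moderate-toxicity trigger therefore decides whether the next patients receive 800 mg/m² at once, or whether 400 or 600 mg/m² is used first. A rule of this kind should give one answer for one set of data. Here it can fail in two ways:

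- The counting unit changes between sentences, so two careful readers can disagree on whether doubling has ended.
- When doubling ends on moderate toxicity alone, one sentence keeps the trial at the current level and the next rule moves it up.

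Under Section 7.2, escalation decisions by the protocol management team need only be noted in its report to the DSMC. Much therefore rests on the written rule.

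**Working it through.** **Stated sizes.** These reproduce and are not in dispute. Section 13.5 gives 3 × 3 + 6 = 15 patients expected and 4 × 6 = 24 at most in phase I. With the 19 new phase II patients, 24 + 19 = 43 overall.

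**Step 1: when the two units disagree.** Let X be the number of qualifying Grade 2 events in a patient, with three assessed patients at 400 mg/m². The patient rule ends doubling if at least two patients have X ≥ 1. The occurrence rule ends it if the events total at least 2. Two affected patients always give two events, so the patient rule implies the occurrence rule. The converse fails in one pattern only: one patient with X ≥ 2 and the other two with X = 0. Any DLT ends doubling under both rules, so the disagreement also needs 0/3 DLTs.

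| Three assessed patients at 400 mg/m² | Counting patients | Counting occurrences |
|---|---|---|
| At most one event in total, 0/3 DLTs | 800 | 800 |
| One patient with ≥ 2 events, others none, 0/3 DLTs | 800 | doubling ended: 400 or 600 |
| Two or three patients with events, 0/3 DLTs | doubling ended: 400 (action sentence) or 600 (0/3 line) | same |
| 1/3 DLTs | doubling ended: three more at 400 | same |

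This assumes exactly three patients. Counting replaced patients, as the synopsis allows, could add further patterns.

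**Step 2: the third row.** The action sentence says "the current dose level will be expanded and the accelerated stage will end; dose-doubling will stop". The list then applies, and its 0/3 line calls for the next dose. With intermediate levels now open, that is 600 mg/m². The note ties both actions to the assessment of three patients, so both can apply to the same data. In the fourth row there is no conflict, because the 1/3 line gives both the action and its size.

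**Step 3: illustration with assumed rates.** The documents give no event rates. Assume X is Poisson with mean m from 0.2 to 1.0, the DLT rate p is 10% to 33%, and patients and event types are independent.

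Row 2 pattern: g(m) = 3 × P(X ≥ 2) × P(X = 0)², multiplied by (1 − p)³.

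- P(X ≥ 2) = 1 − e^(−m)(1 + m) and P(X = 0) = e^(−m).
- g(0.2) = 0.0352, g(0.5) = 0.0996, g(1.0) = 0.1073. The function is not monotone; it peaks inside the range, near m = 0.76, at 0.1161.
- (1 − p)³ = 0.729, 0.512 and 0.296 for p = 10%, 20% and 1/3.
- Lowest: 0.0352 × 0.296 = 1.0%. Middle (m = 0.5, p = 20%): 0.0996 × 0.512 = 5.1%. Highest: 0.1161 × 0.729 = 8.5%.

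Row 3 pattern: with q = 1 − e^(−m), [3q²(1 − q) + q³] × (1 − p)³. This bracket rises with m, so the ends of the range suffice.

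- Lowest: 0.0867 × 0.296 = 2.6%. Middle: 0.3426 × 0.512 = 17.5%. Highest: 0.6936 × 0.729 = 50.6%.

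If three patients are then added after 0/3 DLTs, the chance of 0/6 is again (1 − p)³, or 51% at p = 20%. The result that has no line of its own would therefore be common.

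**The case against.** The strongest reply is that the intent can be recovered. The sentences that prescribe action, in 13.3 and in the synopsis, both count patients; occurrences appear only in descriptive clauses. A single DLT is likewise restated as one patient with a DLT. This stands, and it is the reason to settle on patients. It does not remove the conflict, because one of the occurrence sentences also states what follows once doubling has ended, and no text says which unit governs.

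On the expansion, sentence order favours expanding first. Six is the natural size: every denominator in the list is 3 or 6, the one sized expansion is three more patients, and 13.5 counts six per level. Escalation after 0/6 follows from escalation after 1/6, and 0/6 meets the MTD definition of at most 1/6. This also stands. The size and the missing 0/6 line are gaps that can be filled by inference; the instruction to expand against the 0/3 line is the real conflict.

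A reader might infer three stronger things that the documents do not support:

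- That the sentence "DLT and moderate toxicity incidence will be based on toxicity events encountered during the first cycle of 8-chloro-adenosine treatment" shows that events are to be counted. It covers DLTs and moderate toxicity together and fixes the cycle 1 window. Every DLT rule in 13.3 counts patients, so it cannot imply event counting.
- That the plan is silent on replaced patients with moderate toxicity. The synopsis states the rule, and 13.1 and 13.3 do not contradict it; repeating it there is editorial.
- That the wrong dose is likely. All rates above are assumed. Independence of Grade 2 events and DLTs within a patient is also assumed without support, and 13.2 lets further Grade 2 events be excluded with PI and DSMC approval. The row 3 range is too wide to inform; it shows how often the ambiguity would arise, not how often a wrong dose would follow.

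**Conclusion.** The point holds as a contradiction in the written dosing rule, with an intent that can probably be inferred. The two counting units are not equivalent: with three patients at 400 mg/m² they part in exactly one pattern, where the choice is 800 mg/m² against the end of doubling. With two or more affected patients and 0/3 DLTs, the text supports both staying at 400 and going to 600 mg/m². A single DLT causes no difficulty. These conclusions need no event rate. They do assume that doubling is still open at the 400 mg/m² start and that counting begins there; nothing in 13.1 or 13.3 says otherwise. The 1.0% to 8.5% for the first pattern is illustration only. Because the rule governs the one remaining doubling step and the remedy is wording, it should be corrected.

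**What to change.** (a) Use two patients as the unit in 13.1, 13.3 and the synopsis, matching the sentences that already prescribe the action.

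(b) State in 13.3 that, if two patients have moderate toxicity and none has a DLT, the current level is expanded by three patients, to six, before the DLT rules apply. State that 0 or 1 DLT in six then escalates to the next intermediate level, and that the 0/3 line applies only to cohorts opened after doubling has ended.

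The cost is a few sentences, up to three more patients at 400 mg/m², and the time to assess their first cycle. The stated phase I maximum of 24 counts six at 400 mg/m² but assumes that no intermediate doses are tested. This branch opens them, so 24 is not a cap for it.

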13.4 Recommended Phase II Dose (RP2D)

The MTD will be based on the assessment of DLT during cycle 1 (see section 13.2). The MTD will be defined as the highest dose at which $\leq 1/6$ patients in a cohort experience DLT. The recommended phase II dose (RP2D) of 8-chloro-adenosine will generally be the MTD, but it may be less than the MTD based on a review of available data/cumulative toxicities from phase I.

13.5 Sample Size Accrual Rate

Phase I:

The phase I study will follow a 3+3 design, to evaluate toxicities associated with 8-chloro-adenosine when given as a single agent. Four doses of 8-chloro-adenosine will be tested: dose level 1a: 100 mg/m²; dose level 2a: 200 mg/m²; dose level 3a: 400 mg/m² and dose level 4a: 800 mg/m². Intermediate dose levels, in increments of 50% from the planned four doses, will be explored in the presence of dose limiting toxicity or unacceptable moderate toxicity. Intermediate doses –'b' levels are defined as follows: 150mg/m²; 300 mg/m²; and 600 mg/m². In the phase I portion of this study, the total sample size will depend on the

number of dose levels evaluated to determine the RP2D. While the phase I study is expected to enroll and treat 15 patients (dose levels 1-3 –‘a’ levels, to enroll/treat 3 patients each for a total of 9, and another 6 at dose level 4-assuming the 800 mg/m² dose is well tolerated), a maximum of 24 patients could be treated (6 patients treated at each of the four dose levels) –assuming intermediate doses are not tested.

Phase II:

The phase II portion of the study is expected to enroll a minimum of 9 and a maximum of 25 patients. The six patients treated at the RP2D in the phase I portion of the study will count toward the 25 patients required; given this, we expect to enroll only 19 new patients during the phase II trial portion. The sample size is based on the desire to achieve a (promising) target response rate of >30%.

Clinical Pharmacology (PK/PD):

Pharmacokinetic (PK) will be performed during Cycle 1 in all enrolled patients in Phase 1 and Phase 2 portions of this protocol. In addition, pharmacodynamics measurements will be performed during Cycle 1 in all enrolled patients in the Phase 1 and 2 portions who have ≥ 5000 circulating leukemic blasts per microliter.

Molecular Studies:

For mRNA-seq, sequence reads will be mapped to the human genome (hg19) using TopHat and the frequency of Refseq genes will be counted with customized R scripts. For miRNA-seq, sequences will be adapter trimmed and aligned to hg19 genome using Novoalign, and miRNA expression level will be counted as previously described [1]. The raw counts will then be normalized and compared using the Bioconductor package “edgeR” [2]. Fold changes $>$ than 3 with a false discovery rate (FDR) < 0.05 will be considered significant. Assuming the dispersion of genes across replicates is 0.2, 12 samples in each group (responder vs. non-responder) should have 88% power to detect a 3-fold difference between groups at an FDR level of 0.05.

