Phase I: In the phase I portion of this study, the total sample size will depend on the number of dose levels evaluated to determine the RP2D. While the phase I study is expected to enroll and treat 15 patients (dose levels 1-3 –'a' levels, to enroll/treat 3 patients each for a total of 9, and another 6 at dose level 4a-assuming the 800 mg/m^2 dose is well tolerated), a maximum of 24 patients could be treated (6 patients treated at each of the four dose levels) assuming intermediate doses are not pursued.

Phase II: The phase II portion of the study is expected to enroll a minimum of 9 and a maximum of 25 patients. The six patients treated at the RP2D in the phase I portion of the study will count toward the 25 patients required; given this, we expect to enroll only 19 new patients during the

phase II trial portion. The sample size is based on the desire to ensure a (promising) response rate of 30% is not missed.

Clinical Pharmacology (PK/PD): Pharmacokinetic (PK) analyses will be performed during Cycle 1 in all enrolled patients in Phase 1 and Phase 2 portions of this protocol. In addition, pharmacodynamic measurements will be performed during Cycle 1 in all enrolled patients in the Phase 1 and 2 portions who have ≥ 5000 circulating leukemic blasts per microliter.

Molecular Studies: For mRNA-seq, sequence reads will be mapped to the human genome (hg19) using TopHat and the frequency of Refseq genes will be counted with customized R scripts. For miRNA-seq, sequences will be adapter trimmed and aligned to hg19 genome using Novoalign, and miRNA expression level will be counted as previously described [1]. The raw counts will then be normalized and compared using the Bioconductor package “edgeR” [2]. Fold changes > 3 with a false discovery rate (FDR) < 0.05 will be considered significant. Assuming the dispersion of genes across replicates is 0.2, 12 samples in each group (responder vs. non-responder) should have 88% power to detect a 3-fold difference between groups at an FDR level of 0.05.

Safety Analysis and Stopping Rules for Excessive Toxicity

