1.4 Exploratory Ex-Vivo Molecular Objectives (Phase I and II)

To determine the cytotoxicity of 8-chloro-adenosine toward leukemic progenitor cells in vitro.

To generate a preliminary pre-treatment RNA/miRNA signature in leukemic progenitor cells, and explore its possible association with in vitro cytotoxicity to 8-chloro-adenosine.

To explore the possible association between the preliminary RNA/miRNA signature and clinical response to 8-chloro-adenosine.

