9.2.2 Bone Marrow and PBMC Collection

When feasible an additional 10 ml of bone marrow will be collected in purple-top (EDTA) tube during pre-study evaluation for correlative studies and at the end of cycle 1 and 2 for future studies. If sufficient bone marrow is not collected, PBMC collected from patients with circulating leukemic blasts (via 26 to 30 ml in purple-top (EDTA) tube) will be obtained for analysis. Samples will be gently inverted to mix the sample and then promptly taken to processing by the biospecimen coordinator designated for this study [contact] [name] and send email to [contact] in advance of sampling (ideally at least a day in advance).

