12.2 Response

The primary endpoint is complete remission rate (CR + CRi) and is based on the Döhner, 2010 criteria²⁴; calculated as the percent of evaluable patients that have confirmed CR or CRi.

Response criteria will be as follows:

CR: Bone marrow with < 5% blasts by morphology. ANC > 10³/µL, platelets ≥ 10⁵/µL

CRi: Bone marrow with < 5% blasts by morphology, not meeting blood count criteria for CR.

PR: Decrease of at 50% in bone marrow blasts

PD: Bone marrow blasts more than 20% and increase in blasts by over 50%.

HR: improvement in hematologic parameters, but not meeting criteria for PR.

Secondary activity endpoints for this study are as follows:

- Duration of response, defined as the time interval from the date of first documented response (CR+CRi) to documented disease relapse or death whichever occurs first.
- Overall survival, defined as the time interval from date of first dose of study drug to date of death from any cause.
- Event-free survival, defined as the time interval from date of first dose of study drug to first documented disease progression or death from any cause, whichever occurs first.
- Overall response rate (CR/CRI/PR), calculated as the percent of evaluable patients that have confirmed CR or CRi or PR.

12.3 Clinical Pharmacology Endpoints:

- For plasma PK, levels of 8-chloro-adenosine, its deaminated metabolite, 8-chloro-inosine, and its base 8-chloro-adenine will be quantitated in plasma during 5 days of therapy.
- For cellular PK, concentrations of 8-chloro-adenosine and 8-chloro-ATP will be quantitated in circulating leukemia cells in the peripheral blood.
- For urine PK, levels of 8-chloro-adenosine, its deaminated metabolite, 8-chloro-inosine, and its base 8-chloro-adenine will be quantitated in urine during the first 24 hours of therapy.
- For PD, the impact of therapy on endogenous ATP pools, as well as the effect on short-lived mRNA transcripts and proteins will be analyzed in circulating acute leukemia blasts.

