- To determine if there are dose-dependent changes in 8-chloro-ATP and 8-chloro-adenosine (when administered ex vivo), summary statistics and graphical displays will be generated to descriptively compare accumulation of 8-chloro-ATP and endogenous ATP levels in circulating AML blasts over 5 doses.
- Gene ontology (GO) and pathways will be analyzed using DAVID (Database for Annotation, Visualization, and Integrated Discovery), an online bioinformatic resource for functional interpretation of large lists of genes. Pathways and GO that correlate with response will be sorted by their multiple comparison adjusted p value. Potential miRNA targets will be identified using TargetScan and their functional annotation will be done using DAVID.
- All summaries will be exploratory in nature, with the goal of developing further questions regarding the modulation of therapy, or regarding reasons for efficacy or lack of efficacy.

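### The 88% power for a 3-fold expression difference fits only the FDR criterion; under the plan's own two-part significance rule it is at most about 50%

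*Combined protocol and SAP*

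**What the plan says.** Section 13.5 (Molecular Studies) and the matching paragraph of the Protocol Synopsis set the rule for RNA and miRNA comparisons made in edgeR. The synopsis words it as "Fold changes > 3 with a false discovery rate (FDR) < 0.05 will be considered significant"; section 13.5 has the same two conditions. The design assumption follows: "Assuming the dispersion of genes across replicates is 0.2, 12 samples in each group (responder vs. non-responder"). With those inputs the study "should have 88% power to detect a 3-fold difference between groups at an FDR level of 0.05".

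The power sentence names the FDR level and does not mention the fold-change condition. Neither place says that the condition was left out of the power calculation. Section 1.4 gives the purpose, "To explore the possible association between the preliminary RNA/miRNA signature and clinical response to 8-chloro-adenosine", and section 13.7 limits the ambition: "All summaries will be exploratory in nature, with the goal of developing further questions".

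**The concern.** The effect assumed for power (a true 3-fold difference) is the same number as the cut-off that the estimate must exceed. An estimate centred on 3 falls below 3 about as often as above it, so a rule that requires more than 3 discards about half of such genes before the FDR is considered. A claim of 88% beside that rule cannot be the chance of meeting it.

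What is at stake is how a negative result is read. Someone relying on 88% would conclude that a gene with a true 3-fold difference is rarely missed, and that an empty signature argues against such differences. Under the stated rule, about half or more of those genes would be missed.

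**Working it through.** **Inputs from section 13.5:** negative binomial dispersion 0.2; 12 samples per group; true fold change 3 (ln 3 = 1.0986); FDR 0.05; significance requires fold change > 3 and FDR < 0.05.

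**Not in the documents, so assumed and varied:** mean count *m* in the lower-expressing group, the share of truly different genes, and the per-gene alpha that follows from the FDR.

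**Step 1. Can 88% be reproduced on the FDR criterion alone?** With means *m* and 3*m*, SE(log fold change) = sqrt((1/m + 1/(3m) + 2 × 0.2)/12), and power = Φ(1.0986/SE − z).

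- High counts: SE = sqrt(0.4/12) = 0.1826 and 1.0986/SE = 6.017. Power of 88% needs z = 6.017 − 1.175 = 4.842, a two-sided per-gene alpha of about 1.3e-6.
- *m* = 5: SE = sqrt(0.6667/12) = 0.2357 and 1.0986/SE = 4.661. Power of 88% needs z = 3.486, alpha about 4.9e-4.
- Link to FDR: alpha = power × π × 0.05/((1 − π) × 0.95), where π is the share of truly different genes. For π = 1% and power 0.88 this is 0.00044/0.9405 = 4.7e-4.
- Combinations close to the stated figure: *m* = 5 with π = 1% gives 87.7%; *m* = 10 with π = 0.1% gives 87.2%; *m* = 3 with π = 5% gives 86.6%.

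So 88% is attainable as FDR-only power, although the stated inputs do not fix it.

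**Step 2. The fold-change condition.** P(observed > 3 | true = 3) is about 0.50 for any roughly median-unbiased estimate. Simulating 400,000 pairs of group means per setting gives 49.6% to 50.0% for *m* from 1 to 1000. With a prior count of 0.125, which shrinks the estimate, it is 41% to 50%. Joint power cannot exceed this probability, whatever the missing inputs are.

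**Step 3. Which condition binds?** The smallest observed fold change that passes the FDR criterion is exp(z × SE). At the alpha that gives 88%, this is exp(3.486 × 0.2357) = 2.27 for *m* = 5 and exp(4.842 × 0.1826) = 2.42 at high counts. Both are below 3, so the fold-change filter decides and joint power is 0.50. At low counts with a strict alpha the FDR criterion decides: for *m* = 2 and alpha 1e-5, exp(4.417 × 0.2981) = 3.73, and both powers are low.

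**Step 4. Simulation** (negative binomial counts, dispersion 0.2 treated as known, likelihood-ratio test, 200,000 genes per setting, 12 vs 12, true fold change 3):

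| Mean count, lower group | Per-gene alpha | FDR criterion alone | Two-part rule |
|---|---|---|---|
| 5 | 5e-4 | 0.90 | 0.50 |
| 20 | 1e-5 | 0.87 | 0.50 |
| 100 | 2.5e-6 | 0.87 | 0.50 |
| 2 | 1e-5 | 0.25 | 0.25 |
| 1 | 1e-5 | 0.08 | 0.08 |

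A full Benjamini-Hochberg simulation (20,000 genes, 60 replicates) agrees. FDR-only and two-part power were 0.97 and 0.50 (log-normal means with median 50, 1% of genes different), 0.90 and 0.51 (mean 5, 1%), 0.98 and 0.49 (mean 100, 0.1%), and 0.30 and 0.30 (mean 2, 0.1%).

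**Step 5. Sample size does not help.** At alpha 5e-4, two-part power for means 5 and 100 is 0.11 and 0.26 with 3 per group, and 0.43 and 0.50 with 6. It stays at 0.50 with 24, 100 and 500 per group.

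**Step 6. What true fold change gives 88% under the rule?** Where the filter binds, it is about 3 × exp(1.175 × SE): 3 × exp(1.175 × 0.183) = 3.72 at high counts and 3 × exp(1.175 × 0.236) = 3.96 at *m* = 5. Simulation gives about 3.8 at mean 20 and 4.2 to 4.6 at mean 2, depending on alpha.

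**The case against.** The strongest reply is that the power sentence names its own criterion, an FDR level of 0.05. It can be read as the power of the FDR test, with the fold-change limit acting as a separate reporting filter. Both sentences could then be true and the fault would be one of labelling. It can be added that the 50% follows from placing any cut-off at the assumed effect and says nothing against 12 per group, and that an exploratory analysis with no action tied to a missed gene hardly needs a power figure.

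Much of this stands. FDR-only power is the one workable reading of 88%, no arithmetic error has been shown, and the choice of 12 per group is not in question. It does not remove the point. The sentence just before makes the fold-change limit part of what counts as significant, and nothing tells the reader that the power figure ignores it. Reading the rule instead as a formal test against a 3-fold threshold would lower the power at 3-fold further.

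A fair caution also applies to any restated figure. It depends on mean count and alpha, which the plan does not give, and the simulations treat dispersion as known whereas edgeR estimates it.

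**Conclusion.** The concern holds. The plan states a power that its own significance rule does not deliver: 88% as written, against at most about 50% at a true 3-fold difference, and less where counts are low and the per-gene threshold is strict. The upper bound needs only that the estimated fold change be roughly median-unbiased or shrunk towards no difference. The fold changes of 3.7 to 4.0 needed for 88% also rest on dispersion 0.2, 12 per group and the mean counts named in the working.

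The consequence is confined to the power statement and to the reading of missed genes or an empty signature. It should be corrected because the sentence misinforms as it stands and is easy to repair.

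**What to change.** Keep the rule and change the power sentence in section 13.5 and in the synopsis, in one of two ways.

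- **Relabel.** Say that 88% is power for the FDR criterion alone, before the fold-change filter, and is not the probability that a gene meets the significance rule. This needs no further inputs.
- **Restate.** For example: *With 12 samples per group and dispersion 0.2, power under this rule is at most about 50% for a true 3-fold difference and reaches 88% at a true fold change of about 3.7 (high counts) to 4.0 (mean count 5 in the lower-expressing group).* State the assumed mean count and per-gene alpha, and add that low-count genes need more (about 4.2 to 4.6 at mean 2).

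The cost is one sentence in two places. The analysis, the rule and the sample size do not change; the stated power becomes less favourable or more narrowly labelled.

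As a side note, which does not bear on the verdict, the same edit could say which patients and which definition of responder the 12 per group assumes. Section 1.4 covers both phases. Section 9.2.2 makes the marrow sample conditional ("When feasible an additional 10 ml of bone marrow will be collected"), with blood as the fallback. Section 12.2 has a second response measure that includes PR ("Overall response rate (CR/CRI/PR), calculated as the percent of evaluable patients that have confirmed CR or CRi or PR"). If the response rate were 30% and every patient were sampled, the binomial probability of at least 12 responders would be 4% among 25 patients, 31% among 34 (15 + 19) and 67% among 43. At 35% it would be 13%, 55% and 87%.
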